7.6 Trial Drug Pausation

If a patient experiences an AE, which is considered related to trial drug and which according to the Investigator requires dose pausation, the investigator may decide that the patient should skip the following week's doses (2 doses in total); i.e. the dose interval is increased; however, the injected dose remains the same. In that case, both the doses in the week need to be skipped in order to keep the blind.

If the AE does not abate and it continues to be considered related to trial product, the investigator may decide that the patient should continue to pause treatment but always so that both doses in a week are skipped. If the AE has not abated and the AE continues to be considered related to trial product and is not acceptable based on an overall assessment of benefit and risks, the patient

should be discontinued from the trial treatment but should, to the extent possible, adhere to the planned visit schedule.

The patient may resume treatment if the AE resolves and the Investigator deems it safe and in the patient's best interest to resume treatment. When resuming, the patient should start by taking Vial 1, followed by Vial 2.

If the same type of AE reappears with re-challenge and the nature of the event is not considered acceptable, the dosing should be stopped, but the patient should, to the extent possible, adhere to the planned visit schedule.

An accumulated maximum of 4 weeks of treatment pausation can be allowed. Hereafter, trial treatment should be discontinued (discontinuation due to adverse event) for the remainder of the trial, but patients should be encouraged to attend all remaining visit and complete all required assessments.

7.7 Patient Replacement

Randomized patients who have subsequently withdrawn consent or who have been discontinued from trial treatment will not be replaced.

Rescreening is allowed and can take place after a patient has failed the Optimization and Stabilization Phases (prior to randomization) if the Investigator judges that the patient is clinically stable.

8 Treatment of Patients

8.1 Treatment Assignment and Randomization

Eligible patients will be randomized in a double-blind fashion to 1 of 3 treatment groups in a ratio of 1:1:1:

- Glepaglutide 20 mg per week, administered as 10 mg SC injections twice weekly
- Glepaglutide 10 mg per week, administered as 10 mg SC injection once weekly and placebo SC injection once weekly
- Placebo, administered as SC injections twice weekly

All 3 treatment arms involve twice-weekly dosing (glepaglutide and/or placebo) to maintain the blind. The first dose is taken on Day 1 and the second dose should be taken on either Day 4 or Day 5 of each treatment week (interval chosen at the randomization visit and adhered to throughout the trial period). Please see [Table 3](#) for a schematic overview.

Table 3: Dosing Regimen

Second Dosing 3 Days after Visit 1								
Day	1	4	8	11	15	18	22	...
Dispensing unit	1		2		3		4	
Twice weekly DB treatment	Vial 1	Vial 2	Vial 1	Vial 2	Vial 1	Vial 2	Vial 1	...
Second Dosing 4 Days after Visit 1								
Day	1	5	8	12	15	19	22	...
Dispensing unit	1		2		3		4	
Twice weekly DB treatment	Vial 1	Vial 2	Vial 1	Vial 2	Vial 1	Vial 2	Vial 1	...

Abbreviations: DB=double-blind

The choice of dosing days will be recorded. Both the patient and Investigator will be blinded to the actual content of each vial (active or placebo); therefore, it is important that the patient selects the correct vial for each administration. Randomization will be performed using a block randomization scheme stratified by patient's weekly PS volume requirements (< 12 L per week versus \geq 12 L/week).

The randomization scheme will be generated prior to the initiation of the trial by an independent statistician/programmer who will not be a member of the trial team; Investigators will not be aware of the block size of the randomization scheme.

Patients will be randomly assigned to trial treatments using an automatic, interactive web response system (IWRS), which is integrated into the electronic data capture system (EDC) and has been validated for the intended use under Title 21 of the US Code of Federal Regulations (CFR) Part 11 (FDA regulation for Electronic Records and Electronic Signatures) and the International Council for Harmonisation (ICH) Guidance E6 for Industry on Good Clinical Practice.

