11.1.2 SBS Characteristics and Disease History

Information about the patient's SBS will be obtained at Screening and include the following characteristics:

- The underlying cause of SBS
- Date of diagnosis of underlying disease
- Date of SBS diagnosis
- Remaining bowel sections²⁸; whether patient has a colon-in-continuity (jejuno-colic anastomosis/SBS anatomical group 2, jejuno-ileo-colic anastomosis/SBS anatomical group 3, or other), an end-jejunostomy/SBS anatomical group 1, ileostomy/SBS anatomical group 1, or colostomy, the surgery dates and reason(s) for resection, this includes the most recent resection
- Bowel lengths; length of the remnant small bowel, the remnant colon in percent (according to Cummings classification²⁹)
- Severity of SBS based on the ESPEN Functional and Clinical Classification of Chronic Intestinal Failure⁸
- Date that the patient started PS

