12.3.1 Primary Efficacy Endpoint

The primary efficacy endpoint is the actual reduction in weekly PS volume from baseline to Week 24. Baseline weekly PS volume is defined as the PS volume received during the 7-day period prior to Visit 1 (Day 1), i.e. during the stabilization phase. The Week 1, 2, 4, 8, 12, 16, 20, and 24 weekly PS volume is defined as the PS volume received during the 7-day period prior to these visits.

The primary analysis uses a restricted maximum likelihood (REML)-based repeated-measures approach to compare treatment groups with respect to the mean change from baseline in weekly

PS volume at Week 24. The model will use weekly PS volume assessments at Week 1, 2, 4, 8, 12, 16, 20, and 24, and will include the covariates for treatment group, baseline weekly PS volume, visit (categorical variable), stratification factor (weekly PS volume requirements <12 L/week versus >12 L/week), and visit-by-treatment group interaction. Variance estimation is based on an unstructured covariance matrix, which does not presume a particular correlation structure for repeated weekly PS volume measurements within patients over time. The primary comparison is the difference in the reduction in weekly PS volume from baseline to Week 24 between each glepaglutide treatment group versus placebo.

Following the *Treatment Policy* estimand strategy, missing values will be imputed using multiple imputation methods. For the primary analysis, a *Copy Reference (CR)* approach is used with placebo treatment as reference, while for sensitivity analyses, a *Jump to Reference (J2R)* and a *Copy Incremental from Reference (CIR)* approaches will be applied. Details are described in [Section 12.6](#) and in the SAP.

The Copy Reference approach is justified as the trophic effects on the intestines mediated by glepaglutide would take weeks to abate after treatment withdrawal. A longitudinal growth of the remaining intestines could also have occurred after prolonged therapy and such modifications would not be expected to return fully to the baseline condition. Other effects of GLP-2 agonism, like reduced fluid secretion from the upper part of the GI tract and effects on reducing motility would however be expected to return to the baseline conditions when treatment is withdrawn.

As a supplementary analysis, the analysis will be repeated using the Per-protocol Analysis Set.

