The primary analysis uses a restricted maximum likelihood (REML)–based repeated-measures approach to compare treatment groups with respect to the mean change from baseline in actual weekly PS volume at Week 24. The model will use actual weekly PS volume assessments at Weeks 1, 2, 4, 8, 12, 16, 20, and 24 as an independent variable, and will include the covariates of treatment group, baseline actual weekly PS volume, visit (categorical variable), stratification factor (weekly PS volume requirements <12 L/week versus \geq 12 L/week), and visit-by-treatment group interaction. Variance estimation is based on an unstructured covariance matrix, which does not presume a particular correlation structure for repeated weekly PS volume measurements within patients over time. The primary comparisons are the contrasts (differences in least squares means) between the glepaglutide treatment groups and the placebo group at the Week 24 visit in this mixed-effects model for repeated measures (MMRM).

Missing values will be imputed using multiple imputation methods. For the primary analysis, a Copy Reference (CR) approach is used (main estimator), while for sensitivity analyses, a Jump to Reference (J2R) approach (sensitivity estimator 1) and a Copy Incremental from Reference (CIR) approach (sensitivity estimator 2) will be applied. Details are described in 5.3.1 below.

The Copy Reference approach is justified as the trophic effects on the intestines mediated by glepaglutide would take weeks to abate after treatment withdrawal. A longitudinal growth of the remaining intestines could also have occurred after prolonged therapy, and such modifications would not be expected to fully return to the baseline condition. Other effects of GLP-2 agonism-like reduced fluid secretion from the upper part of the GI tract and effects on reducing motility would, however, be expected to return to the baseline conditions when treatment is withdrawn.

As an additional sensitivity analysis (sensitivity estimator 3), the actual weekly PS volume will be derived using a valid 14-day period prior to the visit. For details on the derivation of actual weekly PS volume within a 14-day period, see Appendix A. This endpoint will be analyzed in the same manner as for the primary analysis for the primary endpoint.

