The number of bowel movements recorded in the eDiary during the 48-hour period prior to baseline and Week 24, and the change from baseline to Week 24 will be presented descriptively. The number of stoma bag emptyings recorded in the eDiary during the 48-hour period prior to baseline and Week 24 will be summarized in a similar manner, for the subset of patients in the FAS who have a stoma.

Measurements of hydrational status

To evaluate the trends on hydration status the urine volume (mL) and the oral fluid intake (mL) recorded by the patients in the eDiary during 48-hour periods prior to the nominal visits will be presented graphically together with the actual weekly PS volume (L/Week) as follows:

- The individual trajectories of 48-hour urine volume (mL), 48-hour oral fluid intake (mL) and weekly PS volume (L) recorded in the patients in the eDiary will be plotted by actual times (start of 48-hour period or visit). Profiles will be gathered in different panels by SBS anatomical classification and treatment group.
- Mean plots of urine volume (mL by 48-hours), oral fluid intake (mL by 48-hours) and actual weekly PS volume (L/Week). Plots by nominal visit and treatment group
 - y1-axis L/Week (for actual weekly PS volume)
 - y2-axis mL/48-hours (for urine volume and oral fluid intake)

25 August 2022

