The remaining, monotone missing data for all patients who discontinue the trial prematurely will be imputed using sequential regression multiple imputation model estimated based on data from the placebo arm only. Each sequential regression model (i.e., for imputation of values at a given time point) will include explanatory variables (treatment group, visit (categorical variable), stratification factor (weekly PS volume requirements <12 L/week versus \geq 12 L/week)), and all previous (Baseline weekly PS volume, Visit at Weeks 1, 2, 4, 8, 12, 16, 20, and 24) values of actual weekly PS volume. Missing values at a given time point in placebo and glepaglutide arms will be imputed from the same imputation model, conditional on patient values observed or imputed at previous time points. No rounding or range restrictions will be applied to imputed continuous values.

Imputed data will consist of 100 imputed datasets. A different and separate random seed number will be used for the partial imputation with the MCMC method, and for the sequential regression multiple imputation. Those random seed numbers are specified in Table 7 below.

	Random seed for imputing monotone missingness (if applicable)	Random seed for imputation of remaining data	Number of imputations
Primary imputation	mary imputation 2125		100

Table 7 Random seeds and number of imputations

Each of the 100 imputed datasets will be analyzed using the following analysis method. Change in actual PS volume from baseline to each post-baseline visit will be calculated based on observed and imputed data. Treatment group comparison at Week 24 will be based on the least squares mean (LSM) difference between glepaglutide groups and placebo in change from 25 August 2022 Confidential Page 34 of 65

baseline in actual PS volume estimated by the analysis model in each of the imputed datasets. Results from analysis of each imputed dataset, i.e., LSM treatment differences and their standard errors, will be combined using Rubin's imputation rules to produce a pooled LSM estimate of treatment difference, its 95% confidence interval, and a pooled p-value for the test of null hypothesis of no treatment effect.

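### No planned analysis of the overall effect adjusts for SBS anatomy, a baseline factor recorded for every patient; the possible cost is some precision, not validity

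*Protocol*

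**What the plan says.** **Randomization.** Protocol 8.1: "Randomization will be performed using a block randomization scheme stratified by patient's weekly PS volume requirements", with a cut at 12 L/week. No other factor is named.

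**Primary model.** SAP 3.1: the MMRM "will include the covariates of treatment group, baseline actual weekly PS volume, visit (categorical variable), stratification factor" and visit-by-treatment. Protocol 12.3.1 gives the same list: "will include the covariates for treatment group, baseline weekly PS volume, visit (categorical variable), stratification factor". Both baseline terms describe PS volume.

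**Imputation.** In SAP 5.3.1 each sequential regression "will include explanatory variables (treatment group, visit (categorical variable), stratification factor", plus earlier PS volumes. There is no anatomy term.

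**Other estimators.** None of the estimators in SAP Table 3 (estimands and missing data) or SAP Table 5 (endpoint derivation) adds a baseline covariate.

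**Anatomy.** Inclusion criteria 7 and 8 (Protocol 7.2) require either a stoma or colon-in-continuity. Protocol 11.1.2 has anatomy recorded before randomization: "Information about the patient's SBS will be obtained at Screening and include the following characteristics", among them "whether patient has a colon-in-continuity (jejuno-colic anastomosis/SBS anatomical group 2, jejuno-ileo-colic anastomosis/SBS anatomical group 3, or other". SAP Table 4 lists anatomy as one of six subgroups. Its footnote defines Group 1 as patients whose CRF shows no colon-in-continuity. SAP 3.5 also uses anatomy to split the SBS-I results and the hydration plots: "Profiles will be gathered in different panels by SBS anatomical classification and treatment group". SAP section 6 tabulates it at baseline.

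**The concern.** The trial admits two anatomically different kinds of patient, and the sponsor thought the distinction worth reporting on. With about 36 patients per arm and no stratification on anatomy, the share with colon-in-continuity will differ between arms by chance. If anatomy predicts the change in PS volume beyond what baseline PS volume already predicts, two things follow. The outcome variance it explains stays in the residual, and in any one trial an imbalance moves the estimated drug effect by an amount the model cannot correct. A pre-specified covariate would address this using data already collected. Without one, an imbalance seen in the baseline table could be handled only by an adjustment chosen after unblinding.

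**Working it through.** **Inputs from the documents** (Protocol 7.1 and 12.7, SAP 2.6): mean changes of -4.5, -4.3 and -2.3 L/week, so differences of 2.2 and 2.0; SD 2.62; two-sided alpha 0.025 per comparison; 108 patients, 36 per arm.

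**Assumptions, because the documents give no figures:** colon-in-continuity share p = 50%; a gap D of 1.0, 1.5 or 2.0 L/week in mean PS change between the anatomical groups, *remaining after* adjustment for baseline PS volume; 2.62 taken as the residual SD of the planned model.

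**1. The plan's own figure.** SE = 2.62 × √(2/36) = 0.618. For two tests sharing a placebo arm (correlation 0.5), the power to succeed with either regimen is 95.8% by normal approximation and 95.3% by simulation with t critical values. The stated figure is 95%. All eight cells of the protocol's power table reproduce within 2 points. Once-weekly alone has 84.1% by normal approximation.

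**2. Chance imbalance.** The SD of the difference in share between two arms is √(2 × 0.5 × 0.5/36) = 0.118, or 11.8 percentage points (10.8 at a 30% share, 11.5 at 60%). By exact binomial calculation at a 50% share, a gap of 20 points or more arises in about 7.6% of active-placebo comparisons.

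**3. What that does to the estimate.**

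| D (L/week) | Variance explained, p(1-p)D²/2.62² | 95% range of chance shift, 1.96 × D × 0.118 |
|---|---|---|
| 1.0 | 0.25/6.864 = 3.6% | ±0.23 |
| 1.5 | 0.5625/6.864 = 8.2% | ±0.35 |
| 2.0 | 1.00/6.864 = 14.6% | ±0.46 |

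The shift and the unexplained variance are one cost, not two. At D = 1 the variance of the shift is 2 × 0.25 × 1²/36 = 0.0139, and variance explained × SE² = 0.0364 × 0.3814 = 0.0139. The planned standard error already contains it.

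**4. Validity without the term.** In a simulated single-visit comparison with D = 1 or 2, the unadjusted analysis has type I error 0.025 and a mean estimate of essentially zero under the null.

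**5. Effect of adjusting.** The empirical SE comes from the same single-visit simulation. Power for the 2.0 L/week difference comes from 6,000 simulated trials of 3 × 36 per value of D. Either-regimen power is by normal approximation, with SD reduced to 2.62 × √(1 - variance explained).

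| D | Empirical SE | Power, 2.0 L/week comparison | Either-regimen power |
|---|---|---|---|
| 0 | see below | 82.4% → 82.0% | 95.8% (no change) |
| 1.0 | 0.618 → 0.610 | 83.0% → 84.0% | 95.8% → 96.4% |
| 1.5 | not simulated | 82.8% → 85.7% | 95.8% → 97.1% |
| 2.0 | 0.618 → 0.575 | 82.4% → 87.5% | 95.8% → 97.9% |

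At D = 0 the model-based SE rises from 0.616 to 0.619, and 0.003/0.616 = 0.5%. At D = 0.5 the variance explained is 0.25 × 0.25/6.864 = 0.9%, which lowers the SE by about 0.5%. The gain then roughly equals the cost of estimating the factor.

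**The case against.** The strongest reply is that this is a modelling choice and not an error. Nothing in either document says anatomy predicts PS change beyond baseline PS volume, and the gaps used here are assumed. The largest equals the whole assumed once-weekly effect. That stands, and it is why the benefit can be given only as a range.

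Three stronger readings are tempting and are not supported:

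- *That the primary estimate is biased, the error rate inflated or the trial underpowered.* Randomization protects the unadjusted contrast, the planned interval already includes the chance shift, and the stated power reproduces.
- *That the SAP treats anatomy as its key subgroup.* Table 4 does not rank its six subgroups. Anatomy is the only disease-specific one, the rest being age, sex, race, ethnicity and region, but that does not show it to be prognostic.
- *That randomization should have been stratified on anatomy.* Covariate adjustment deals with the same imbalance in the analysis, and the allocation scheme need not change.

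It can also be said that imbalance will be visible in the baseline table and that the subgroup MMRM (SAP 3.1.2) models anatomy. Both are true, but the table adjusts nothing, and the subgroup model gives within-subgroup estimates without formal testing. Neither alters the primary contrast.

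Lastly, the 0.5% cost comes from a single-visit linear model. The eight-visit MMRM with unstructured covariance, and imputation regressions fitted on about 36 placebo patients, were not simulated. That caveat stands.

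**Conclusion.** The omission is real and its consequence modest. PS volume is the only baseline characteristic in the randomization, the primary MMRM and the imputation models, and no planned estimator of the overall effect uses anatomy. What may be lost is precision, together with correction of a chance imbalance. Under a 50% share and a residual gap of 1.0 to 2.0 L/week, the Week 24 standard error would fall by about 1% to 7% (0.008/0.618 to 0.043/0.618). Single-comparison power would rise from about 83% to 84-87.5%, and either-regimen power from about 96% to 96-98%. Below a gap of about 0.5 L/week there is no net gain. The single-comparison figure matters because the gatekeeping procedure tests each regimen in its own right. This is a worthwhile refinement with a small expected cost; leaving it out does not undermine the trial's conclusions.

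**What to change.** Before unblinding, amend SAP 3.1 and 5.3.1 and record the change in SAP section 8:

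- Add a two-level factor, colon-in-continuity as recorded in the CRF (no = SAP Group 1, yes = all other categories), and its interaction with visit to the primary MMRM. The yes/no coding avoids sparse categories. The same model then serves the Week 12 key secondary endpoint.
- Add the factor as a main effect to the imputation models.
- Leave randomization unchanged. Leave the CMH tests unchanged too: SAP 3.2 already needs a fallback for empty cells with one stratification factor, and a second would make such cells more likely. The binary key secondary endpoints therefore stay unadjusted for anatomy.

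The cost is SAP wording, a few degrees of freedom, and one more predictor in regressions fitted on the placebo arm alone. No new data are needed, and Protocol 12.1 lets the SAP override the protocol's analysis text. If the sponsor prefers not to alter the primary model, naming the same model as an extra sensitivity estimator in SAP Table 3 is a lesser alternative. It would show the influence of any imbalance but would not improve the primary test.

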8.2 Trial Drug Administration

Glepaglutide and placebo are delivered as ready-to use liquid formulation in vials. Patients will use single-use syringes, provided by Zealand Pharma, to withdraw 0.5 mL solution from a vial of drug product and inject it SC. Patients must choose their preferred injection site area; either on their abdomen or their thigh(s). Unless otherwise agreed with the Investigator, patients must use this selected injection site area during the entire trial. The specific injection site must be rotated for each weekly injection such that the injections are administered at least 5 cm away from the last injection administered, and still within the same injection site area, i.e., abdomen or thigh. It is acceptable to inject in 1 thigh or both thighs during the Treatment Phase.

The initial dose of trial drug will be administered by a trial staff member at the first visit (Day 1). The patient will be instructed by trial staff on the preparation, administration, storage, and return of trial drug at the Day 1 visit. Patients will be instructed to report the DUN (Dispensing Unit Number) and date and time of the day of trial drug administration. If dosing is on the same day as the visits (and in the morning), the trial drug should not be administered at home before

visiting the site as the trial drug is taken at the trial site shortly after the PK and ADA and other lab sampling and assessments.

